8.1.2 Definition of Serious Adverse Events (SAE)

Serious Adverse Event

Adverse events are classified as serious or non-serious. A **serious adverse event** is any AE that is:

- fatal
- life-threatening
- requires or prolongs hospital stay
- results in persistent or significant disability or incapacity
- a congenital anomaly or birth defect
- an important medical event

Important medical events are those that may not be immediately life threatening, but are clearly of major clinical significance. They may jeopardize the subject, and may require intervention to prevent one of the other serious outcomes noted above. For example, drug overdose or abuse, a seizure that did not result in in-patient hospitalization or intensive treatment of bronchospasm in an emergency department would typically be considered serious.

All adverse events that do not meet any of the criteria for serious should be regarded as **non-serious adverse events**.

8.1.3 Definition of Unanticipated Problems (UP)

Unanticipated Problems Involving Risk to Subjects or Others

Any incident, experience, or outcome that meets all of the following criteria:

- Unexpected in nature, severity, or frequency (i.e. not described in study-related documents such as the IRB-approved protocol or consent form, the investigators brochure, etc.)
- Related or possibly related to participation in the research (i.e. possibly related means there is a reasonable possibility that the incident experience, or outcome may have been caused by the procedures involved in the research)
- Suggests that the research places subjects or others at greater risk of harm (including physical, psychological, economic, or social harm).

CONFIDENTIAL

8.2 Classification of an Adverse Event

8.2.1 Severity of Event

For AEs not included in the protocol defined grading system, the following guidelines will be used to describe severity.

- **Mild** – Events require minimal or no treatment and do not interfere with the participant's daily activities.
- **Moderate** – Events result in a low level of inconvenience or concern with the therapeutic measures. Moderate events may cause some interference with functioning.
- **Severe** – Events interrupt a participant's usual daily activity and may require systemic drug therapy or other treatment. Severe events are usually potentially life-threatening or incapacitating.

8.2.2 Relationship to Study Agent

The clinician's assessment of an AE's relationship to study is part of the documentation process, but it is not a factor in determining what is or is not reported in the study. If there is any doubt as to whether a clinical observation is an AE, the event should be reported. All AEs must have their relationship to study agent assessed. In a clinical trial, the study product must always be suspect. To help assess, the following guidelines are used.

- **Related** – The AE is known to occur with the study agent, there is a reasonable possibility that the study agent caused the AE, or there is a temporal relationship between the study agent and event. Reasonable possibility means that there is evidence to suggest a causal relationship between the study agent and the AE.
- **Not Related** – There is not a reasonable possibility that the administration of the study agent caused the event, there is no temporal relationship between the study agent and event onset, or an alternate etiology has been established.

For all collected AEs, the clinician who examines and evaluates the participant will determine the AE's causality based on temporal relationship and his/her clinical judgment. The degree of certainty about causality will be graded using the categories below.

- **Definitely Related** – There is clear evidence to suggest a causal relationship, and other possible contributing factors can be ruled out. The clinical event, including an abnormal laboratory test result, occurs in a plausible time relationship to drug administration and cannot be explained by concurrent disease or other drugs or chemicals. The response to withdrawal of the drug (dechallenge) should be clinically plausible. The event must be pharmacologically or phenomenologically definitive, with use of a satisfactory rechallenge procedure if necessary.
- **Probably Related** – There is evidence to suggest a causal relationship, and the influence of other factors is unlikely. The clinical event, including an abnormal laboratory test result, occurs within a reasonable time after administration of the drug, is unlikely to be attributed to concurrent disease or other drugs or chemicals, and follows a clinically reasonable response on withdrawal (dechallenge). Rechallenge information is not required to fulfill this definition.
- **Possibly Related** – There is some evidence to suggest a causal relationship (e.g., the event occurred within a reasonable time after administration of the trial medication). However, other factors may have contributed to the event (e.g., the participant's clinical condition, other concomitant events). Although an AE may rate only as "possibly related" soon after discovery, it can be flagged as requiring more information and later be upgraded to "probably related" or "definitely related," as appropriate.
- **Unlikely to be related** – A clinical event, including an abnormal laboratory test result, whose temporal relationship to drug administration makes a causal relationship improbable (e.g., the event did not occur within a reasonable time after administration of the trial medication) and in which other drugs or chemicals or underlying disease provides plausible explanations (e.g., the

CONFIDENTIAL

- participant's clinical condition, other concomitant treatments).
- **Not Related** – The AE is completely independent of study drug administration, and/or evidence exists that the event is definitely related to another etiology. There must be an alternative, definitive etiology documented by the clinician.

8.2.3 Expectedness

The Principal Investigator will be responsible for determining whether an AE is expected or unexpected. An AE will be considered unexpected if the nature, severity, or frequency of the event is not consistent with the risk information previously described for the study agent.

8.3 Time Period and Frequency for Event Assessment and Follow-Up

The occurrence of an AE or SAE may come to the attention of study personnel during study visits and interviews of a study participant presenting for medical care, or upon review by the DSMB. All AEs including local and systemic reactions meeting the criteria for SAEs will be captured on the appropriate CRF. Information to be collected includes event description, time of onset, clinician's assessment of severity, relationship to study product (assessed only by those with the training and authority to make a diagnosis), and time of resolution/stabilization of the event. All SAEs occurring while on study must be documented appropriately regardless of relationship. All SAEs will be followed to adequate resolution.

Any medical condition that is present at the time that the participant is screened will be considered as baseline and not reported as an AE. However, if the study participant's condition deteriorates at any time during the study, it will be recorded as an AE. UPs will be recorded in the data collection system throughout the study.

Changes in the severity of an SAE will be documented to allow an assessment of the duration of the event at each level of severity to be performed. SAEs characterized as intermittent require documentation of onset and duration of each episode.

The PI will record all reportable events with start dates occurring any time after informed consent is obtained until 30 days (for SAEs) after the last day of study participation. At each study visit, the investigator will inquire about the occurrence of SAEs since the last visit. Events will be followed for outcome information until resolution or stabilization.

All unresolved serious adverse events should be followed by the investigator until the events are resolved, the subject is lost to follow-up, or the adverse event is otherwise explained. At the last scheduled visit, the investigator should instruct each subject to report any subsequent event(s) that the subject, or the subject's personal physician, believes might reasonably be related to participation in this study. The investigator should notify the study sponsor of any death or adverse event occurring at any time after a subject has discontinued or terminated study participation that may reasonably be related to this study. The sponsor should also be notified if the investigator should become aware of the development of cancer or of a congenital anomaly in a subsequently conceived offspring of a subject that has participated in this study.

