3.1 Primary Objective

This pilot feasibility study is being conducted to determine safety and efficacy of the strategy of transplantation of lungs from HCV positive donors (with or without evidence of active HCV viremia) into HCV-negative recipients on the NYU Langone Health lung transplant waiting list, with subsequent anti-HCV therapy to treat infection in the recipient.

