6.1.9 Tracking of Dose

While in the hospital, nursing staff will give any doses and accountability will be maintained in the electronic medical record. Once outpatient, patients will attend regularly scheduled clinic appointments for routine care following a lung transplant and medication review will occur on each of these visits to ensure that the medication is being taken properly. Laboratory testing for HCV will be performed as described. Clearance of HCV and SVR will serve as clinical evidence that the medication is being taken properly.

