7.2 Laboratory Procedures/Evaluations

7.2.1 Clinical Laboratory Evaluations

The following tests will be reviewed for patients who are included in the study but will be performed as standard of care for lung transplant recipients:

- **Hematology:** hemoglobin, hematocrit, white blood cells (WBC) with differential count, platelet count
- **Biochemistry:** sodium, potassium, CO₂, BUN, creatinine, total bilirubin, alanine aminotransferase (ALT), aspartate aminotransferase (AST), alkaline phosphatase
- **Coagulation:** INR
- **Pregnancy test,** usually to be done within 24 hours prior to study intervention and results must be available prior to administration of study product.
- **HBV quantitative (Hepatitis B Virus DNA, quantitative Real-Time PCR) testing:** PCR test for detection and quantification of HBV viral load, an indicator of active HBV infection. These tests are performed as standard of care for patients who receive transplanted organs from a donor who is designated "PHS increased infectious risk." By definition, all HCV positive organ donors meet criteria for designation as PHS increased infectious risk.
- **HBV serologic testing (HBsAb, HBsAg, HBcoreAb):** serologic testing to evaluate for the presence of immunity to HBV or the evidence of prior infection with HBV. These tests are performed as standard of care for patients who receive transplanted organs from a donor who is designated "PHS increased infectious risk." By definition, all HCV positive organ donors meet criteria for designation as PHS increased infectious risk.
- **HIV serologic testing (HIV1 and 2 antigen/antibody 4th gen):** serologic testing to evaluate for the presence of HIV infection. These tests are performed as standard of care for patients who receive transplanted organs from a donor who is designated "PHS increased infectious risk." By definition, all HCV positive organ donors meet criteria for designation as PHS increased infectious risk.

The following tests will be performed specifically for purposes of this study:

- **HCV genotyping:** to be performed on all donors in parallel with (not prior to) the transplant, and to be performed for any recipient who develops HCV viremia post-transplant. Donor serum will be sent to Quest Laboratories for this testing (Hepatitis C Viral RNA, Genotype, LiPA[®]). Recipient testing for HCV genotyping will be ordered by standard ordering procedures through Epic as with all other tests.

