8.4 Reporting Procedures – Notifying the IRB

8.4.1 Adverse Event Reporting

All AEs will be recorded in AE CRFs by a member of the study team. AEs will be recorded within 3 business days of the study team being made aware of the AE. The relationship of the AE to the study interventions will be noted by the PI. AEs that are deemed definitely related or probably related to the study interventions will be reported to the IRB and the DSMB within 3 days of their designation as such. The DSMB will determine the need for an emergency meeting between the DSMB and the study team (see

CONFIDENTIAL

safety oversight below). AEs that are deemed unrelated or not likely related to the study interventions will be recorded on CRFs as described above and will be reviewed at quarterly DSMB safety review meetings, and at annual review by the IRB.

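### The only visit inquiry stated in section 8.3 covers SAEs, while section 8.4.1 requires all AEs to be recorded, so symptomatic non-serious events are likely to be under-ascertained

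*Combined protocol and SAP*

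**What the plan says.** The primary objective (3.1) joins two aims: "This pilot feasibility study is being conducted to determine safety and efficacy of the strategy of transplantation of lungs from HCV positive donors".

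Section 8.3 describes how events are found. It opens broadly: "The occurrence of an AE or SAE may come to the attention of study personnel during study visits and interviews of a study participant", with DSMB review as a further route. On what is written down it says: "All AEs including local and systemic reactions meeting the criteria for SAEs will be captured on the appropriate CRF". The one question that it gives the investigator is narrower: "At each study visit, the investigator will inquire about the occurrence of SAEs since the last visit".

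Section 8.4.1 sets the recording duty: "All AEs will be recorded in AE CRFs by a member of the study team". The clock is 3 business days from the team learning of the event. AEs judged definitely or probably related go to the IRB and DSMB within 3 days of that judgement. Those judged unrelated or unlikely to be related are reviewed at the quarterly DSMB meetings. Section 8.6 repeats the quarterly review of non-emergent AEs.

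The Section 19 schedule has rows for history, examination, vital signs, Mavyret start and follow-up, HCV PCR, serology and genotyping. It has no row for adverse events.

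**The concern.** The duty to record is wider than the duty to ask. Section 8.4.1 covers every AE, but its clock starts only when the team knows of the event, and the question in 8.3 would not bring a non-serious event to light. How many are found then depends on how forthcoming the patient is and how closely a given clinician enquires, so the count is both low and uneven.

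Tolerability matters here. Mavyret is given for 8 weeks beside post-transplant drugs, and for some patients crushed through a nasogastric tube (6.1.4). Section 5.7.2 plans for patients who stop because of intolerance. Problems short of an SAE are part of what a safety objective should describe, and the DSMB can review only what has been recorded or reported to it.

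**Working it through.** The plan gives no figure on this point, so the main check is to set the sections side by side.

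1. **What is asked.** 8.3 names SAEs only. No other systematic question about AEs was found in the available text.
2. **What must be recorded.** 8.4.1: all AEs. The two sections do not match.
3. **Whether the schedule closes the gap.** Section 19 has no AE row. Medical history and physical examination are marked only at POD0 and POW52. From POW1 to POW24 the scheduled items are HCV PCR and serology, genotyping once viremic, and Mavyret start and follow-up.
4. **Which other routes exist.**
   - Laboratory review (7.2.1): "The following tests will be reviewed for patients who are included in the study but will be performed as standard of care". The panel includes ALT, AST, bilirubin, creatinine and blood counts. It can show mild liver or blood-count changes, but not symptoms such as nausea or fatigue.
   - Clinical observation (8.2.2): "If there is any doubt as to whether a clinical observation is an AE, the event should be reported". This says what to do with an observation once made; it does not require a question.
   - Medication review (6.1.9): "medication review will occur on each of these visits to ensure that the medication is being taken properly". Its stated purpose is adherence.
   - Interviews at care contacts and DSMB review (8.3). These may reveal events, but neither is a systematic solicitation.
5. **Whether the AE definition removes the issue.** 8.1.1 confines AEs, for this protocol, to events tied to Mavyret treatment. Non-serious Mavyret-related events remain inside that definition, and the visit question leaves them out.

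**Illustration of size.** Let n be the number treated, p the true incidence of a non-serious event, and a the share of such events that is ascertained by any route. The probability of seeing the event at least once is 1 − (1 − p·a)^n. Section 10.5 supports two values of n: 14 (70% of 20) and the 7 that it also states. The values of p and a are assumptions.

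| n | p | a = 1 | a = 0.5 | a = 0.25 |
|---|---|---|---|---|
| 14 | 0.20 | 1 − 0.80^14 = 96% | 1 − 0.90^14 = 77% | 1 − 0.95^14 = 51% |
| 14 | 0.10 | 1 − 0.90^14 = 77% | 1 − 0.95^14 = 51% | 1 − 0.975^14 = 30% |
| 7 | 0.20 | 1 − 0.80^7 = 79% | 1 − 0.90^7 = 52% | 1 − 0.95^7 = 30% |
| 7 | 0.10 | 1 − 0.90^7 = 52% | 1 − 0.95^7 = 30% | 1 − 0.975^7 = 16% |

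Halving ascertainment has the same effect as halving the incidence. The table shows how sensitive so small a study is to lost reports; it does not estimate what this trial will lose.

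**The case against.** A reader might infer that non-serious events are picked up only if the patient volunteers them. The documents do not support that. Laboratory results are reviewed, doubtful clinical observations are reportable, events may emerge in care interviews, and 8.3 requires deterioration of a baseline condition to be recorded as an AE. This objection stands in full for laboratory-detectable events, including mild liver changes. It stands only in part for symptoms.

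A reader might also infer that the protocol contains no AE question anywhere. That cannot be shown. The table of contents lists 7.2.4 and 7.3.1 to 7.3.6, where visit content would normally be described, and most of that text is absent from the copy available for this review. The surviving fragment mentions Mavyret intolerance and the documentation of AEs and SAEs. Missing text is not a fault of the plan. If a question does sit there, 8.3 would still need to agree with it.

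The capture sentence in 8.3 can be read as limited to events that meet SAE criteria. That reading is weak: 8.4.1 settles that all AEs are recorded, so the sentence needs tidying rather than correcting in substance.

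Finally, no AE rate is an endpoint (4.2) or a planned summary (10.4.1). The halting rules in 8.5 turn on related deaths and on SAEs, with treatment failure added in 10.4.2. This is right, and it limits the consequence: the primary endpoint, SVR, is untouched.

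**Conclusion.** The concern holds as a mismatch between 8.3 and 8.4.1. The inquiry stated in 8.3 covers SAEs, the recording duty covers all AEs, and neither the schedule nor the rest of the available text supplies a systematic question about non-serious events. Symptomatic non-serious events are therefore likely to be under-ascertained and unevenly collected. That weakens the safety half of a joint safety and efficacy objective; safety is not the sole primary objective.

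The size is unknown. The probabilities in the table rest on assumed incidences and ascertainment shares and on 14 or 7 treated patients. It would go too far to conclude that the DSMB will see a falsely clean record, because the documents give no ascertainment rate and the other routes will find some events. The conclusion is also conditional on the absent parts of 7.2.4 to 7.3.6 not containing an AE inquiry. On that footing, the change is worth making because it is cheap and removes an inconsistency.

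**What to change.** In 8.3, make three changes:

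- Widen the visit question to name both AEs and SAEs since the previous visit. Put it as one standard, non-leading question at each study visit already held.
- Reword the capture sentence so that every AE is captured on the CRF whether or not it meets the SAE criteria. Sections 8.3 and 8.4.1 then agree.
- Check the new wording against the visit descriptions in 7.3.

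At the same time, reconcile the AE definition in 8.1.1 with 8.3. The former excludes post-consent conditions unrelated to the study medication; the latter requires SAEs to be documented regardless of relationship. Until that is settled, wider questioning will not give a consistent AE record. An AE row in Section 19 against those visits would make the requirement visible.

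The cost is a few sentences and more AE CRF entries, mainly in the early post-transplant weeks. The question should not be imposed on every Section 19 contact. Outpatient blood may be processed at local laboratories (7.2.3), so some contacts may be blood draws without an investigator present, and asking there might need extra staff time.

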8.4 Reporting Procedures – Notifying the IRB

8.4.1 Adverse Event Reporting

All AEs will be recorded in AE CRFs by a member of the study team. AEs will be recorded within 3 business days of the study team being made aware of the AE. The relationship of the AE to the study interventions will be noted by the PI. AEs that are deemed definitely related or probably related to the study interventions will be reported to the IRB and the DSMB within 3 days of their designation as such. The DSMB will determine the need for an emergency meeting between the DSMB and the study team (see

CONFIDENTIAL

safety oversight below). AEs that are deemed unrelated or not likely related to the study interventions will be recorded on CRFs as described above and will be reviewed at quarterly DSMB safety review meetings, and at annual review by the IRB.

8.4.2 Serious Adverse Event Reporting

All SAEs will be recorded in SAE CRFs by a member of the study team. SAEs will be recorded within 3 business days of the study team being made aware of the SAE. The relationship of the SAE to the study interventions will be noted by the PI. SAEs that are both unexpected and deemed related to the study interventions will be reported to the IRB and the DSMB within 24 hours of the PI designation as such. The DSMB will determine the need for an emergency meeting between the DSMB and the study team (see safety oversight below) or whether these can be reviewed at quarterly meetings. SAEs that are deemed unrelated or not likely related to the study interventions will be recorded on CRFs, will be reported to IRB and DSMB within 3 days of their designation as such and will be reviewed at quarterly DSMB safety meetings.

8.4.3 Unanticipated Problem Reporting

Incidents or events that meet the OHRP criteria for UPs require the creation and completion of an UP report form. It is the site investigator's responsibility to report UPs to their IRB and notify the DSMB. The UP report will include the following information:

- Protocol identifying information: protocol title and number, PI's name, and the IRB project number;
- A detailed description of the event, incident, experience, or outcome;
- An explanation of the basis for determining that the event, incident, experience, or outcome represents an UP;
- A description of any changes to the protocol or other corrective actions that have been taken or are proposed in response to the UP.

To satisfy the requirement for prompt reporting, UPs will be reported using the following timeline:

- UPs that are SAEs will be reported to the IRB within 3 days the investigator becoming aware of the event.
- Any other UP will be reported to the IRB within 3 days of the investigator becoming aware of the problem.

